15.5.1 Analysis of the primary efficacy variable

The primary efficacy analysis will be the comparison between bimekizumab and placebo in the proportion of subjects achieving HiSCR at Week 12, although the model used will analyze data from all three treatment groups. The number and percentage of subjects who achieved HiSCR at Week 12 will be presented by treatment group and the statistical analysis of this variable will be conducted following a Bayesian paradigm utilizing an informative prior on both the placebo and adalimumab group response rates where these informative priors were derived from published summary data (Clinical Study Protocol M11-810 - PIONEER II). A vague prior will be assumed for the bimekizumab treatment group.

The Bayesian analysis of HiSCR at Week 12 will employ a logistic regression model including treatment group (placebo, adalimumab, and bimekizumab) and adjusting for Baseline Hurley Stage.

The posterior distributions of the treatment group response rates together with 95% credible intervals for all three treatment group response rates, and of the difference in response rates between the treatment groups will be summarized. A 95% credible interval will be presented for the bimekizumab versus placebo comparison and a 60% credible interval will be presented for the bimekizumab versus adalimumab comparison. This latter comparison of bimekizumab with adalimumab is an informal one to assess whether any improvements in response rate observed with bimekizumab (over placebo) are comparable to the current standard of care and will be used for internal decision making on the future development of the compound. This comparison will not be part of the evaluation of Proof of Concept for this study. The posterior probability that the difference in response rates between the placebo and bimekizumab treatment groups is greater than zero will also be presented.

The study will be considered a success if the posterior probability that the difference in response rates between the placebo and bimekizumab groups being greater than zero is at least 97.5% (ie, the lower bound of the 95% credible interval of the difference between bimekizumab and placebo in HiSCR rates is greater than or equal to zero).

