2.4 Determination of sample size

The predefined success criterion for declaring a positive study requires a posterior probability of at least 97.5% that the HiSCR rate at Week 12 for bimekizumab will be higher than that for placebo.

Additionally, the study has an exploratory objective to informally compare bimekizumab against the current standard of care for HS (adalimumab) using the 60% credible interval for the treatment difference.

Sample size calculations are based on the number of subjects required to meet the above success criterion (comparing against placebo) assuming a true underlying HiSCR rate at Week 12 of 70% for bimekizumab. Published data from the PIONEER I and II studies (Kimball et al, 2016a) indicate that, when antibiotic therapy at entry is allowed, the response rates for placebo and adalimumab at Week 12 are 27.6% and 58.9% respectively.

Using simulation, it is estimated that with data from 40 subjects on bimekizumab, 20 subjects on placebo and 20 subjects on adalimumab (80 subjects total), the study will provide at least a 99% probability of meeting the success criterion and an 80% probability of meeting the exploratory criterion under the assumptions described below.

These simulations were based on Bayesian augmented control models in which the published summary data were used to construct informative priors for the placebo and adalimumab treatment arms in the current study. Based on historic data, the Bayesian model assumes an informative prior distribution for the placebo group HiSCR rate to be $\beta(5.52, 14.48)$. This prior distribution contributes an approximate effective sample size of 20 subjects for the placebo treatment group. Similarly, the Bayesian model assumes an informative prior distribution for the adalimumab group HiSCR rate to be $\beta(11.78, 8.22)$ which, with the parametrization in the model, is equivalent to an adalimumab response rate of 58.9%. This prior distribution contributes an approximate effective sample size of 20 subjects for the adalimumab group. For the bimekizumab HiSCR rate, a vague prior probability distribution $N(0, 1E4)$ was assumed.

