4 STATISTICAL/ANALYTICAL ISSUES

4.1 Adjustments for covariates

Randomization will be stratified by Baseline Hurley Stage in this study. Accordingly, all statistical models fitted in the analyses of the primary efficacy variable will include the stratification factor for Baseline Hurley Stage as a covariate.

In cases of classification errors at the time of randomization, subjects may be assigned to an incorrect stratum. In these cases, subjects will be included in the statistical modelling according to the observed values of Baseline Hurley Stage regardless of the value used by the site to stratify the subject at randomization.

Concomitant antibiotic use at entry into the study will be included as an additional covariate in the supportive and sensitivity analyses of the primary efficacy variable.

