8.2.2.1 Bayesian modeling

The primary Bayesian model (a logistic regression model for the mean binary response $E[y]$) will be:

$$\ln\left(\frac{E(y)}{1-E(y)}\right) = \beta_{PBO} X_{PBO} + \beta_{BKZ} X_{BKZ} + \beta_{ADA} X_{ADA} + \beta_{hII} X_{hII} + \beta_{hIII} X_{hIII} \quad (1)$$

where X_{PBO} , X_{BKZ} and X_{ADA} are dummy variables taking the value 1 or 0 according to whether or not each subject is in the PBO, BKZ or ADA treatment groups respectively, X_{hII} and X_{hIII} are dummy variables taking the value 1 or 0 according to whether or not each subject is in the Baseline Hurley Stage II or III groups respectively. Proof-of-concept (PoC) will be declared in this study if the estimated posterior probability, using the above model, of the difference in response rates between the BKZ and PBO treatment groups is 0.975 or greater.

For parameter estimation, the following constraint will be used:

$$\beta_{hII} = -\beta_{hIII}$$

giving the model:

$$\ln\left(\frac{E(y)}{1-E(y)}\right) = \beta_{PBO} X_{PBO} + \beta_{BKZ} X_{BKZ} + \beta_{ADA} X_{ADA} + \beta_{hII} (X_{hII} - X_{hIII}) \quad (2)$$

so that the influence of Baseline Hurley Stage on the model estimated treatment group mean responses are more evident. To see this, note that if $\bar{\eta}_{PBO}$ represents the mean of the logit responses from model (2) for the PBO subjects (the simple “arithmetic” mean) then $\text{logit}^{-1}(\bar{\eta}_{PBO})$ is the response probability associated with that mean logit response and is 1 type of estimate of the PBO group response rate. Accordingly:

- $p_{PBO} | p_{hII}^{PBO}, p_{hIII}^{PBO} = \text{logit}^{-1}(\bar{\eta}_{PBO}) = \text{logit}^{-1}(\beta_{PBO} + \beta_{hII}(p_{hII}^{PBO} - p_{hIII}^{PBO}))$ represents the probability of response in the PBO group conditional on p_{hII}^{PBO} and p_{hIII}^{PBO} , which are the Baseline Hurley Stage subject proportions chosen to evaluate the estimated PBO group mean at (here the observed proportions are chosen)
- $p_{BKZ} | p_{hII}^{BKZ}, p_{hIII}^{BKZ} = \text{logit}^{-1}(\bar{\eta}_{BKZ}) = \text{logit}^{-1}(\beta_{BKZ} + \beta_{hII}(p_{hII}^{BKZ} - p_{hIII}^{BKZ}))$ represents the probability of response in the BKZ group conditional on p_{hII}^{BKZ} and p_{hIII}^{BKZ} which are the Baseline Hurley Stage subject proportions chosen to evaluate the estimated BKZ group mean at (here again the observed proportions are chosen)

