- $p_{ADA} | p_{hII}^{ADA}, p_{hIII}^{ADA} = \text{logit}^{-1}(\bar{\eta}_{ADA}) = \text{logit}^{-1}(\beta_{ADA} + \beta_{hII}(p_{hII}^{ADA} - p_{hIII}^{ADA}))$ represents the probability of response in the ADA group conditional on p_{hII}^{ADA} and p_{hIII}^{ADA} which are the Baseline Hurley stage subject proportions chosen to evaluate the estimated ADA group mean at (once more here the observed proportions are chosen)

For brevity, and unless otherwise stated the dependence of the above treatment group response rates on the chosen Baseline Hurley Stage subject proportions will be suppressed by denoting them as p_{PBO} , p_{BKZ} and p_{ADA} .

For pragmatic reasons we will ignore the Hurley stage proportions and effects in the equations for the estimated group response rates and use the following relations to map between the probability scale priors for the group response rates and the logit scale treatment group parameters

$$p_{PBO} = \text{logit}^{-1}(\beta_{PBO}) \quad (3)$$

$$p_{ADA} = \text{logit}^{-1}(\beta_{ADA}) \quad (4)$$

The expectations of the prior distributions for the PBO and ADA group response rates will be set to match the observed treatment group response rates in the PII study.

Accordingly, the priors to be used are

$$p_{PBO} \sim \beta(5.52, 14.48) \quad (5)$$

$$\beta_{BKZ} \sim N(0, 10000)$$

$$p_{ADA} \sim \beta(11.78, 8.22)$$

$$\beta_{hII} \sim N(0, 10000)$$

which have expectations equal to 28% and 59% for the PBO and ADA groups respectively to match the observed treatment group response rates of the PIONEER II study. The implicit assumption using this simple approach is that $E_{\beta_{hII}}[\beta_{hII}(p_{hII}^{BKZ} - p_{hIII}^{BKZ})] \approx 0$. It is important to recognize that even if the proposed study also observes a similar Baseline Hurley Stage effect size and subject proportions as the PIONEER II study the priors (5) and equations (3) and (4), whilst yielding estimated treatment group response rates that should be consistent with those observed in the data, may cause the estimated logit coefficients β_{PBO} and β_{ADA} to be inaccurate.

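### The bimekizumab-placebo difference behind the 97.5% rule compares response rates taken at each arm's own Hurley mix, so chance Hurley imbalance re-enters a contrast meant to be adjusted

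*SAP*

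**What the plan says.** Protocol 15.5.1 describes a Bayesian logistic regression with treatment group "and adjusting for Baseline Hurley Stage". SAP 4.1 puts Baseline Hurley Stage into every model of the primary variable. It adds that, after a stratification error, "subjects will be included in the statistical modelling according to the observed values of Baseline Hurley Stage".

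SAP 8.2.2.1 then turns the fitted coefficients into response rates. Placebo is evaluated at the placebo shares, "which are the Baseline Hurley Stage subject proportions chosen to evaluate the estimated PBO group mean at (here the observed proportions are chosen". Bimekizumab is evaluated at its own shares, "chosen to evaluate the estimated BKZ group mean at (here again the observed proportions are chosen", and adalimumab likewise. The next paragraph only shortens the notation: the dependence of the "response rates on the chosen Baseline Hurley Stage subject proportions will be suppressed by denoting them as" p_PBO, p_BKZ and p_ADA.

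SAP 2.4 says success "requires a posterior probability of at least 97.5% that the HiSCR rate at Week 12 for bimekizumab will be higher than that for placebo". SAP 8.2.2.1 ties this to the model: proof of concept needs a posterior probability "of the difference in response rates between the BKZ and PBO treatment groups is 0.975 or greater". No section names a common Hurley mix for that difference. The primary analysis set is the Per-Protocol Set (PPS; SAP 8.2.2).

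**The concern.** A covariate adjusts a comparison only if both arms are evaluated at the same covariate values. Here the Hurley effect is estimated, but each arm is then placed at its own Hurley mix. Any difference in mix goes straight into the difference in rates.

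Stratified randomisation limits the imbalance among randomised subjects but does not remove it from the analysis. PPS exclusions come after randomisation, and mis-stratified subjects are analysed at their observed stage. In a placebo arm of 20, one reclassified subject moves the Stage II share by 1/20 = 5 points. At stake is whether part of the quantity compared with 97.5% is Hurley imbalance rather than drug effect.

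**Working it through.** **Inputs from the documents.** 40, 20 and 20 subjects; rates 70% (bimekizumab), 27.6% (placebo) and 58.9% (adalimumab); priors Beta(5.52, 14.48) and Beta(11.78, 8.22), each worth about 20 subjects; vague priors otherwise (SAP 2.4 and 8.2.2.1).

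**Assumed, because the documents give no values.** Stage II versus III log odds ratio d = 0.8 (range 0.5 to 1.2); 50:50 Hurley mix; PPS loss 10-20%; mis-stratification 0-5%.

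**1. The plan's own figure.** Exact enumeration over Binomial(40, 0.70) and Binomial(20, 0.276) with the placebo prior gives a 98.7% probability of success. SAP 2.4 states at least 99%, so the set-up reproduces.

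**2. Algebra.** In model (2), logit(p) = beta_arm + beta_hII (X_hII - X_hIII), so d = 2 x beta_hII. Let q be an arm's Stage II share, so its II-minus-III share is 2q - 1. Then

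logit(p_BKZ) - logit(p_PBO) = (beta_BKZ - beta_PBO) + 2 x beta_hII x (q_BKZ - q_PBO).

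The first term is the adjusted contrast. The second is Hurley imbalance, and it vanishes when both arms are evaluated at the same q.

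**3. Size of the shift with no treatment effect.** It is approximately p(1 - p) x d x imbalance.
- 10-point imbalance, d = 0.8: 0.276 x 0.724 x 0.08 = 1.6 points at p = 27.6%; 0.25 x 0.08 = 2.0 points at p = 50%. Over d = 0.5 to 1.2: 1.0 to 3.0 points.
- 20-point imbalance: 3.2 to 4.0 points at d = 0.8, and 2.0 to 6.0 over the range.

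**4. How large the imbalance may be.** With intact stratified blocks (size 4 or 8 assumed), the 95th percentile of the bimekizumab-placebo difference in Stage II share is about 4-6 points. It is about 10-11 points after 10% random PPS loss and 14-15 after 20%. Adding 0-5% mis-stratification, the mean is 4-7 points and the 95th percentile 10-18.

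**5. At the threshold.** Take 40 bimekizumab subjects, and 20 placebo subjects plus 20 from the prior. At rates near 48.4% and 27.6%, the standard deviation of the difference is sqrt(0.484 x 0.516/40 + 0.276 x 0.724/40) = 10.6 points, and 27.6 + 1.96 x 10.6 = 48.4. A 1.6-point shift is 0.15 standard deviations. It moves 97.5% to 96.5% or 98.3%, depending on its sign.

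**6. False success at a fixed imbalance favouring bimekizumab.** Three-arm model with the SAP priors, both arms at 27.6%, 3,000 simulated trials per row, standard error about 0.2-0.3 points:

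| Stage II share, bimekizumab vs placebo | Odds ratio II vs III | Own mix | Common mix |
|---|---|---|---|
| 55% vs 45% | 2 | 1.7% | 1.2% |
| 55% vs 45% | 3 | 1.8% | 0.9% |
| 60% vs 40% | 2 | 2.8% | 1.0% |
| 60% vs 40% | 3 | 3.0% | 0.9% |

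**7. Averaged over random imbalance.** False success is about 0.9-1.2% at own mix and 0.8-1.0% at a common mix. The success decision differs between the two in about 0.3-0.4% of trials with no effect, about 1% at a 70% bimekizumab rate and about 5% at 55%. The probability of success at 70% differs by less than half a point.

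**The case against.** The strongest counter-argument is in SAP 8.2.2.1 itself. The sentence introducing equations (3) and (4) says the Hurley proportions and effects will be set aside in the equations for the estimated group rates. The assumption stated later, that the Hurley term is about zero, is written with the bimekizumab shares. If (3) and (4) defined the reported rates and were extended to bimekizumab, every rate would be the inverse logit of beta_arm, an implied 50:50 mix, and the contrast would be adjusted. Some ambiguity therefore stands. It is not the natural reading: the same sentence gives the purpose as mapping priors to logit parameters, only placebo and adalimumab have an equation, and the SAP then expects the estimated rates to agree with the data while the coefficients may be inaccurate, which fits own-mix rates.

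A reader might infer that the Hurley covariate achieves nothing, or that the protocol's commitment is broken outright. The documents do not support that. Protocol 15.5.1 and SAP 4.1 speak of the model, and beta_BKZ - beta_PBO is adjusted for Hurley stage.

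Other analyses also help. The Full Analysis Set repeat (SAP 8.2.3.1) removes imbalance caused by PPS exclusions, the GEE odds ratios control for Hurley stage (SAP 8.2.3.7), and HiSCR is tabulated by Hurley stage (SAP 8.2.5). A material imbalance would be visible, but none of these feeds the 97.5% rule.

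**Conclusion.** The point holds on the natural reading of SAP 8.2.2.1: the coefficients are Hurley-adjusted, but the rate difference that decides proof of concept is not. For each 10 points of imbalance, the shift is about 1-3 points and can favour either arm.

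A reader might infer from the 60% versus 40% rows that the rule's false-success rate exceeds 2.5%. That does not follow. Those rows fix a 20-point imbalance in bimekizumab's favour, beyond the 95th percentile of 10-18 points under the assumed losses. Averaged over random imbalance, the rate stays near 1%, and the success probability of roughly 99% is not threatened. The consequence is confined to a result near the threshold or an unlucky imbalance.

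The Hurley effect, Hurley mix, block size, PPS loss and mis-stratification rate are all assumptions, and losses are taken as random. The existence of the extra term rests on none of them; its size does.

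**What to change.** In SAP 8.2.2.1, evaluate p_PBO, p_BKZ and p_ADA at one common Hurley distribution, that of the pooled analysis set. At each posterior draw, average logit^-1(beta_arm + beta_hII) and logit^-1(beta_arm - beta_hII) using the pooled Stage II and III shares as weights. Base the difference, its credible interval and the 97.5% rule on these rates. State that equations (3) and (4) serve only the prior mapping.

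The model has no treatment-by-Hurley interaction, so the sign of the difference at each draw is that of beta_BKZ - beta_PBO whatever common mix is used. The choice of mix affects the size and interval of the difference, not the 97.5% rule.

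This is a free improvement: one line of code and a few words in the SAP, with no new data. Timing needs care. Sponsor personnel review unblinded interim results (SAP 4.5.2), and this amendment already draws on the second interim analysis (SAP 3.9). Document the change with its reason and report the own-mix calculation alongside it.

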8.2.2.2 Building the prior

From the PIONEER II data, despite the strength of any interaction within treatment groups between antibiotic use and Baseline Hurley Stage being unknown, it is valid to pool the data across Baseline Hurley Stages within these groups to obtain estimates of the overall group response rates and their variability, and to use this information as the basis for building informative priors for the PBO and ADA treatment groups. In this respect, and from the reported event counts and subject numbers within each Baseline Hurley Stage group, we obtained the following Beta distributions that could be used to describe the observed group response rates in that study:

$$p_{PBO} \sim \beta(45,118)$$

$$p_{ADA} \sim \beta(48,67)$$

After heavily discounting the above priors we obtain the priors given in [Section 8.2.2.1](#).

If further information (independent to this study) regarding the PBO and/or ADA treatment group response rates comes to light then the priors for this analysis may be updated prior to study unblinding, and details of this will be supplied in an amendment to this SAP or the CSR. In this case the priors will still be based upon historic data only.

Note that the informative priors for the PBO and ADA treatment group response rates may be updated based upon any observed differences in the proportions of Baseline Hurley Stage II and III subjects as long as no response rate data from the current study, blinded or unblinded, are taken into consideration. For example, if updated, these priors may be fitted by Baseline Hurley Stage if the relative proportions of Baseline Hurley Stage II and III subjects within the current study differ substantially from those reported in the historical data. In this case the priors will still be based only on historic response data, but using the Hurley-stage specific information rather than the average information.

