If necessary, the results of any planned DMC and/or interim analysis may be shared with key Sponsor's personnel in order to facilitate additional Clinical Planning or Portfolio Management decisions. The results will include both individual and summary results, and will be presented unblinded. All individuals seeing unblinded data will be documented in the Trial Master File.

Further details are provided in the study manuals and site blinding plan.

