If further information (independent to this study) regarding the placebo and/or adalimumab treatment group response rates comes to light subsequent to writing this protocol then this study may be updated prior to study unblinding, and details of this will be supplied in the SAP and the CSR. Note that the informative priors for the placebo and adalimumab treatment group response rates may be updated based upon any observed differences in the proportions of Baseline Hurley Stage II and III subjects as long as no response rate data from the current study, blinded or unblinded, have been taken into consideration. For example, if updated, these priors may be fitted by Baseline Hurley Stage if the relative proportions of Baseline Hurley Stage II and III subjects

within the current study differ substantially from those reported in the historical data. In this case the priors will still be based only on historic response data, but using the Hurley-stage specific information rather than the average information.

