3.9 Changes to protocol-defined analyses

The following changes relative to the protocol-defined analyses have been included in the SAP:

- The protocol defines the HiSCR as “at least a 50% reduction from Baseline in the total abscess and inflammatory nodule count, with no increase from Baseline in abscess or draining fistula count”. The SAP defines this as “at least a 50% reduction from Baseline in the total abscess and inflammatory nodule count, with no increase from Baseline in abscess **or draining tunnels (fistulas/sinus tracts) count**”

- The section on the determination of the sample size in the protocol states that, with the planned sample size of 80 subjects, the probability of study success is 85%. Subsequent simulations have been performed and the probability found to be 99%. The SAP thus states this 99% probability in [Section 2.4](#) instead.
- The PD-PPS was included as an additional analysis set in the SAP and was not part of the clinical study protocol. This was added as it was deemed appropriate to review protocol deviations separately in relation to these data and to define a separate analysis set accordingly.
- The definition of the FAS was updated to include all subjects with a valid Baseline measurement and a post-Baseline measurement for at least 1 efficacy variable. In the protocol, the definition included only subjects with a valid Baseline measurement and a post-Baseline measurement for the primary efficacy variable. Since the primary efficacy variable is a composite endpoint based on abscess count, inflammatory nodule count and draining tunnel (fistula/sinus tract) count, using this definition, any subjects with at least 1 missing component of the composite endpoint would not be included in any of the efficacy analyses.
- Based on the second interim analysis for this study, additional exploratory efficacy variables based on the lesion count assessment data, HiSCR depth and disease flare status, have been defined in this SAP amendment. [Section 8.2.4](#) includes details on the derivation of different HiSCR depths and [Section 8.2.5](#) describes the planned summaries of this additional variable. [Section 8.3.1.2](#) defines disease flare and includes details on planned summaries of disease flare status and the number of visits at which a subject experienced a disease flare during the Treatment Period.

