4.5.2 Interim analysis

This study will include two informal unblinded interim analyses, the first after approximately 45 subjects have completed 4 weeks of the study and the second when the last randomized subject for this study has completed the Week 12 Visit at the end of the Treatment Period or this subject's participation has ended prematurely. This second planned interim analysis excludes the 2 subjects from site 101 who entered the study outside of the recruitment period. The purpose of these interim analyses is for sponsor key personnel to review results from the primary efficacy analysis and a subset of the analyses of exploratory efficacy and safety outcomes to facilitate additional Clinical Planning or Portfolio Management decisions. Neither interim analysis will lead to any formal decision to alter or terminate the trial.

Details on the summaries and analyses to be presented at these informal interim analyses are included in the Interim Analysis SAP.

All analyses and unblinding instructions will be pre-specified in the Interim Analysis SAP.

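### The deadline for updating the primary-analysis priors is undefined, and the SAP written after the second unblinded interim still leaves the update open

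*SAP*

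**What the plan says.** - **Update on new information.** SAP 8.2.2.2 allows new placebo and adalimumab priors if independent information appears: "then the priors for this analysis may be updated prior to study unblinding, and details of this will be supplied in an amendment" to the SAP or, alternatively, in the CSR. Protocol 15.5.1 is worded more loosely ("then this study may be updated prior to study unblinding") and asks for the details in both the SAP and the CSR.
- **Update on Hurley Stage mix.** Both documents also allow the priors to be refitted by Hurley Stage if the Stage II/III mix differs substantially from the historical data. No deadline is attached to this route.
- **Limits on content.** For new information, the SAP says "In this case the priors will still be based upon historic data only". For the Hurley route, an update is allowed "as long as no response rate data from the current study, blinded or unblinded, are taken into consideration".
- **Interims.** SAP 4.5.2: "This study will include two informal unblinded interim analyses", "the second when the last randomized subject for this study has completed the Week 12 Visit at the end of the Treatment Period" or has stopped early, leaving out two subjects from one site. Key sponsor personnel review the primary efficacy analysis at both. Protocol 7.9 says of results shared with them: "The results will include both individual and summary results, and will be presented unblinded".
- **Date of this SAP version.** SAP 3.9: "Based on the second interim analysis for this study, additional exploratory efficacy variables based on the lesion count assessment data" were added. This version therefore postdates that interim and drew on it.
- **Success rule.** A posterior probability of at least 97.5% that the bimekizumab HiSCR rate exceeds placebo, with a placebo prior of Beta(5.52, 14.48) worth about 20 subjects (SAP 2.4).

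**The concern.** The placebo prior carries about as much weight as the 20 placebo subjects, so the success call depends on it. A prior protects the threshold only if it is chosen without knowledge of the result. Limiting the content of an update to historic data does not achieve this. Someone who knows the Week 12 counts can still decide whether an external study is worth adopting, whether the Hurley mix differs enough to refit, and how heavily to discount the new source. The SAP calls the present priors heavily discounted but gives no rule for setting a discount, so any update needs a fresh choice. Allowing the change to be recorded only in the CSR would let it first appear in writing beside the results.

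**Working it through.** **1. Is the window open?** SAP 3.5.5 speaks of unblinding at each interim and at the final analysis, so the term covers several events. SAP section 1 uses a different cut-off, database lock, for changes to analysis definitions. If study unblinding meant the first interim, the permission would already have lapsed when this version was written. The text nevertheless still grants it in the present tense. The natural reading is that the final unblinding is meant, which falls after the second interim.

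**2. Method.** Inputs are 40 bimekizumab and 20 placebo subjects, the 97.5% threshold, and planning rates of 70% and 27.6% (SAP 2.4). Hurley Stage is ignored, so the adalimumab prior does not enter. With y responders of n, a Beta(a, b) prior gives the posterior Beta(a + y, b + n − y). Bimekizumab has Beta(0.5, 0.5) in place of the vague logit-scale prior; Beta(0.01, 0.01) gives the same calls. P(bimekizumab > placebo) is found by numerical integration.

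**3. The plan's own figure.** Summing binomial probabilities over all outcomes at 70% versus 27.6%, the stated prior gives a success probability of 0.989 (0.987 with Beta(0.01, 0.01)). This matches the SAP's 99% to rounding.

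**4. Effect of the prior on borderline results.** The outcomes, the 35%-centred prior and the size-40 prior are assumptions. Beta(45, 118) is the SAP's own undiscounted prior. With 22/40 responders the bimekizumab posterior is Beta(22.5, 18.5).

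| Outcome | Placebo prior | Placebo posterior | P(bimekizumab > placebo) | Call |
|---|---|---|---|---|
| 22/40 vs 7/20 | Stated, Beta(5.52, 14.48) | Beta(12.52, 27.48) | 98.5% | success |
| 22/40 vs 7/20 | Same size, mean 35%, Beta(7, 13) | Beta(14, 26) | 96.6% | fail |
| 22/40 vs 8/20 | Stated, Beta(5.52, 14.48) | Beta(13.52, 26.48) | 97.4% | fail |
| 22/40 vs 8/20 | Same mean, size 40, Beta(11.04, 28.96) | Beta(19.04, 40.96) | 99.0% | success |
| 22/40 vs 8/20 | Undiscounted, Beta(45, 118) | Beta(53, 130) | 99.9% | success |

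The stated and undiscounted priors have the same mean (5.52/20 = 45/163 = 27.6%), so in the last three rows only the weight changes. The 97.4% is 0.9738 unrounded, close enough to 0.975 that a simulation could fall on either side.

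**5. How often would the call change?** At the planning rates, replacing the stated prior by the 35%-centred one changes the call in about 1.5% of trials, and by the size-40 one in about 0.9%. At assumed true rates of 55% versus 35%, the figures are about 16% and 14%.

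**The case against.** The plan has real safeguards:

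- Both update routes exclude this trial's responses from a new prior.
- Protocol 15.11 keeps the unblinded team from disclosing to the blinded team. Protocol 7.9 requires everyone who sees unblinded data to be documented.
- SAP 4.5.2 says that neither interim leads to a formal decision to alter the trial.
- A vague-prior analysis (SAP 8.2.3.4) and frequentist analyses (SAP 8.2.3.7 to 8.2.3.10) would expose a result driven by the prior.
- The outcomes in the table were picked near the threshold, and this is a Phase 2 proof-of-concept rule.

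All of this stands, and it limits the size of the problem. It does not close the gap. The safeguards govern what enters a prior and who receives results. They do not say who decides on an update. SAP 3.9 shows that interim results did reach the content of the SAP. The sensitivity analyses do not determine success.

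A reader might infer more than the documents support:

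- *That a prior was changed after the results were seen.* In the SAP amendment log, Change #4 shows both Beta priors identical before and after.
- *That the sponsor gave itself new freedom after the interim.* The wording added by Change #13 follows Protocol Amendment 1, whose rationale treats the first interim as still to come.
- *That the trial's own responses may shape the prior.* Both routes forbid it.

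**Conclusion.** The concern holds as one about timing and about who decides. The text leaves the primary-analysis priors open to update after key sponsor personnel have reviewed nearly complete unblinded Week 12 results, and no passage requires the decision or the discount to be made blind to them. This undermines the 97.5% criterion when the result is borderline, where a moderate change in the centre or weight of the placebo prior can reverse the call. It does not empty the criterion of meaning: near the planned effect the call would change in roughly 1 to 1.5% of trials under the two assumed priors.

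The figures rest on a Beta-binomial model without the Hurley term and on assumed outcomes and alternative priors. Beta(45, 118) shows how much the discount matters. It is not itself a change that the update clause invites without new information. The conclusion that the window is open rests on reading study unblinding as the final unblinding, which is the reading that fits a SAP written after the second interim.

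**What to change.** In protocol 15.5.1 and SAP 8.2.2.2, state that the primary-analysis priors are fixed at Beta(5.52, 14.48) for placebo and Beta(11.78, 8.22) for adalimumab, as specified before the first unblinded interim data cut, subject only to the prior-data-conflict rule in SAP 8.2.2.3. Report any prior based on later external or Hurley-specific information only as a labelled supplementary analysis beside the primary one. Delete the SAP's option to record a change in the CSR instead of an amendment; protocol 15.5.1 already expects both.

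The conflict rule needs the explicit exception because it replaces a prior with a vague one after looking at current-study data, so an unqualified freeze would contradict it. That rule relies on graphs without a numerical threshold. Freezing the priors does not settle that separate matter.

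The cost is wording only. The downside is that external data appearing later cannot enter the primary analysis.
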